4.0 TREATMENT

4.1 Treatment:

This is a phase I dose escalation study adding BYL719 to standard capecitabine and radiation.

Capecitabine: 825mg/m²/BID Sunday night through Friday morning on radiation days (See appendix H for capecitabine dosage per BSA)

Dosing: Sunday evening –Friday morning (the night before to the morning of each chemo treatment, not Monday AM-Friday PM): Dose 1 to be taken Sunday PM, then Monday –Thursday AM/PM dosing, then last dose Friday AM.

Radiation: 50.4 Gy, 180 cGY/fraction x 28 fractions:

BYL 719: BYL719 will be given once daily po, from Day 1 of radiation to the final treatment with radiation. BYL719 will be administered orally once daily on a continuous dosing schedule and dosed on a flat-fixed dose and not adjusted by body weight or body surface area.

Missed doses of BYL 719 are not made up and BYL719 will be stopped when radiation is completed.

IF RADIATION IS NOT GIVEN SECONDARY TO TOXICITY OR TOXICITY RECOVERY (OR PER PROTOCOL) ETC, THEN PATIENT IS TO BE INSTRUCTED TO NOT TAKE CAPECITABINE OR BYL719 DRUGS. IF RADIATION IS NOT GIVEN SECONDARY TO A HOLIDAY OR AN ADMINISTRATIVE REASON (MACHINE IS DOWN, SNOW STORM, SCHEDULING ETC) THEN CAPECITABINE IS TO BE HELD (ONCE IT IS KNOWN TREATMENT WON'T BE GIVEN, AS DRUG IS TO BE GIVEN WITH RADIATION). BYL719 HOWEVER, IS STILL TO BE GIVEN AS TREATMENT IS ON A CONTINUOUS BASIS AND REASON IS NOT FOR TOXICITY (BUT MUST BE STOPPED ONCE RADIATION ENDS).

Surgery will be performed approximately 6-10 weeks after the last treatment of BYL719/capecitabine + Radiation

No of pts	Dose Level*	Cohort Level*	Capecitabine	Radiation.
3-6	1	BYL719 200 mg/day	Capecitabine, 825mg/m2 BID Sunday PM-Fri AM	50.4 GY RT
3-6	2	BYL 719 250 mg/day	Capecitabine, 825mg/m2 BID Sunday PM-Fri AM	50.4 GY RT
3-6	3	BYL 719 300 mg/day	Capecitabine, 825mg/m2 BID Sunday PM-Fri AM	50.4 GY RT

(Dose Level -1: 150mg/day, to be used if dose level 1 is not tolerated based on DLTs or in the case when a dose reduction may be needed for a patient on dose level 1.

Only 1 dose reduction is permitted per patient for criteria noted in section 5)

Three patients will be accrued to level 1. If dose level 1 is not tolerated then dose level -1 will be investigated. If no dose limiting toxicities are observed following completion of BYL719, capecitabine and radiation, and after patients are observed for 2 weeks post completion, then accrual to level 2 will proceed. If a DLT is observed in one of the first 3 patients in a dose level, then accrual for that level will be expanded to 6 patients. Two or more instances of DLT in a cohort of 6 patients will result in the preceding dose level being defined as the MTD. After determination of the MTD, the final cohort will be expanded so that a total of 24 patients are treated on study. A patient will be considered inevaluable if they receive <67% of their total intended treatment (BYL719, Capecitabine or Radiation) for non-protocol required reasons.

During the MTD dose finding portion, patients who are removed from study for reasons other than a DLT, defined in section 5.2, will be replaced.

If a dose limiting toxicity occurs, BYL719 will be held until the toxicity reduces to \leq grade 1 at which point patients will be permanently dose reduced by 1 dose level. Patients may continue to receive their capecitabine and radiation as per institutional standard of care when toxicities resolve to \leq grade 2.

If treatment is held for more than 28 days, then patient should come off study. Definition of Dose Limiting Toxicities

- Grade 4 neutropenia (ANC < 500/mm³)
- ANC $<1000/\text{mm}^3$ with fever (temp > 101) or infection
- Grade 4 thrombocytopenia: Platelets <25,000/mm³
- Platelets <50,000/mm³ requiring transfusion
- Grade 3 or 4 treatment related non-hematologic toxicities excluding alopecia. Grade 3 nausea, vomiting or diarrhea will only be considered a dose limiting toxicity if it occurs for greater than 48 hours despite maximal medical support. Grade 3 electrolyte abnormalities will not be considered dose limiting toxicities if the electrolyte disorder can be corrected to grade 2 or less within 72 hours. A grade 4 electrolyte abnormality will be considered a DLT.
- Patients who receive < 67% of intended BYL719 or capecitabine secondary to treatment related toxicities will also be considered as having a DLT (patients will be considered inevaluable)

The investigator or responsible site personnel should instruct the patient to take the study drugs as per protocol (promote compliance). Drug accountability must be performed on a regular basis. Patients will be instructed to return unused study drugs to the site at the end. The site personnel will ensure that the appropriate dose of each study drug is administered at each visit and will provide the patient with the correct amount of drugs for subsequent dosing.

The following general guidelines should be followed for BYL719 administration:

- Patients should be instructed to take the dose (one or more tablets) of BYL719 with a glass of water (~250 ml or ~8 fluid ounces) daily in the morning and within approximately 1 hour after a meal (like breakfast) or snack
- Take BYL719 at approximately the same time each day after a meal or snack (preferable in the morning after breakfast) (recommended 8AM +/1 hour)
- If, for any reason, a breakfast (or other meal) was not consumed, then the patient should take study treatment with a glass of water within 1 hour after a snack that same day. If the patient forgets to take study treatment during the daytime it should be taken in the evening at the latest within 1 hour after a meal, but not later than 6 pm. If not taken by this time, the dose should be withheld that day. Missed doses should not be made up the next day.
- Patients should be instructed to swallow the tablets and not to chew or crush them. However for
 patients with swallowing dysfunction without G tube, BYL719 film-coated tablets can be
 administered as drinkable suspension by crushing the tablets and suspending them in water. The
 drinkable suspension prepared from the film-coated crushed tablets is not permitted for
 administration into feeding tubes.
- Patients should record if the dose was taken or not in the patient diary
- If vomiting occurs during the course of treatment, no re-dosing of the patient is allowed before the next scheduled dose. The occurrence and frequency of any vomiting and/or diarrhea (or increase stool frequency) during the treatment must be noted in the adverse events section of the patient record.

- Patients must avoid consumption of Seville orange (and juice), grapefruit or grapefruit juice, grapefruit hybrids, pummelos, starfruits and cranberry juice from 7 days prior to the first dose of study drug and during the entire study treatment period due to potential CYP3A interaction. Regular orange (Citrus X sinensis) juice is allowed.
- Patients must avoid concomitant intake of strong CYP3A inhibitors and inducers.

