4.2.2 Prohibited concomitant therapy

Other anticancer therapy

If a patient, enrolled in the study, requires the concomitant use of any medication included in Appendix G entitled "List of Prohibited Medications during BYL719 Treatment" (i.e., drugs that are generally accepted by the Qtdrugs.org Advisory Board of the Arizona CERT to have a **known** risk of causing TdP), BYL719 administration must be interrupted as long as the patient requires therapy with the QT prolonging agent. Note Appendix G also prohibits drugs that are substrates for CYP3A and CYP2C with a possible or conditional risk for TdP. If the patient requires long term therapy with such a QT prolonging agent, leading to study treatment interruption of > 28 days, the patient must be permanently discontinued from BYL719.

Herbal medications

Herbal preparations/medications are not allowed throughout the study. These herbal medications include, but are not limited to: medical marijuana, St. John's wort, Kava, ephedra (ma huang), gingko biloba, dehydroepiandrosterone (DHEA), yohimbe, saw palmetto, and ginseng. Patients should stop using these herbal medications 7 days prior to first dose of study drug.

Warfarin and coumarin derivates

Therapeutic doses of warfarin sodium (Coumadin®) or any other coumarin-derivative anticoagulants are not permitted. Warfarin has a narrow therapeutic range and BYL719 is a possible inhibitor of CYP2C8 and 2C9, the major metabolizing enzyme of warfarin. Therapeutic anticoagulation may be accomplished using low-molecular weight heparin.

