5.2 Definition of Dose Limiting Toxicities

- Grade 4 neutropenia (ANC < 500/mm³)
- ANC $<1000/\text{mm}^3$ with fever (temp > 101) or infection
- Grade 4 thrombocytopenia: Platelets <25,000/mm³
- Platelets <50,000/mm³ requiring transfusion
- Grade 3 or 4 treatment related non-hematologic toxicities excluding alopecia. Grade 3 nausea, vomiting or diarrhea will only be considered a dose limiting toxicity if it occurs for greater than 48 hours despite maximal medical support. Grade 3 electrolyte abnormalities will not be considered dose limiting toxicities if the electrolyte disorder can be corrected to grade 2 or less within 72 hours. A grade 4 electrolyte abnormality will be considered a DLT.
- Patients who receive < 67% of intended BYL719 or capecitabine secondary to treatment related toxicities will also be considered as having a DLT

During the MTD dose finding portion, patients who are removed from study for reasons other than a DLT, defined in section 5.2, will be replaced.

5.3 Management of Specific Toxicities are outlined below for all patients: most conservative assessments must be used for management and modification:

If a dose limiting toxicity occurs, BYL719 will be held until the toxicity reduces to \leq grade 1 at which point patients will be permanently dose reduced by 1 dose level. Patients may continue to receive their capecitabine and radiation as per institutional standard of care when toxicities resolve to \leq grade 2.

If treatment is held for more than 28 days, then patient should come off study.

During the MTD dose finding portion, patients who are removed from study for reasons other than a DLT, defined in section 5.2, will be replaced.

For toxicities other than dose limiting toxicities, specific dose adjustments, based on the worst preceding toxicity as graded by the NCI Clinical Toxicity Criteria ([NCI-CTCAE version 4.03]), are described below. A maximum of 1 dose reduction of BYL719 from the starting dose may be allowed.

Missed doses of BYL 719 are not made up and BYL719 will be stopped when radiation is completed.

Dose Modifications for BYL719 (TREATMENT RELATED (BYL719)): This table only applies once patient has begun treatment on study and it is only applicable while they are receiving treatment on study		
Worst toxicity (CTCAE 4.03 Grade)	Dose Modifications for BYL719	
HEMATOLOGICAL		
Neutropenia (ANC)		
Grade 3 (ANC < 1.0 - 0.5 x 10 ⁹ /L)	Omit dose until resolved to ≤ Grade 1, then:	

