All other AEs not noted above (T	reatment Related to BYL719):	
All other AEs (this pertains to no	n-lab AEs only)	
Grade 1 or 2	Maintain dose level	
Grade 3	Omit dose until resolved to ≤ Grade 1, then reduce BYL719 by 1 dose level	
	Note: Omit dose for \geq Grade 3 vomiting or \geq Grade 3 nausea only if the vomiting or nausea cannot be controlled with optimal antiemetic treatment as per local practice.	
Grade 4	Permanently discontinue patient from BYL719	
	Note: Omit dose for \geq Grade 3 vomiting or \geq Grade 3 nausea only if the vomiting or nausea cannot be controlled with optimal antiemetic treatment as per local practice.	

Management of Pneumonitis in patients receiving BYL719

All patients will be routinely asked about and observed for the occurrence of adverse events including new or changed pulmonary symptoms (consistent with lung abnormalities). Patients who are suspected to have 2/15/15, 2/19/15, 3/20/15, 3/27/15,4/23/15, 6/11/15, 6/11/15, 8/14/15, 8/17/15, 8/26/15, 8/31/15, 9/3/15, 9/8/15 approved Novartis, 29 2/11/15, 2/14/15,

9/11/15, 9/14/15, 9/21/15, RNEXECPI 9/29/15, 10/5/15 novartis, 10/6/15 approved Novartis, 10/8/15, 10/19/12 sent FDA, 11/4/15 clinical hold, 11/5/15 sent Novartis, SMP 11/6/15, 11/20/20/15, Amendment # 1 5/6/16, Amendment # 2 6/2/16, Amendment # 3 10/31/16 –FDA Reviewer edits, Amendment #3 updated 1/19/2017, Amendment # 4 6/20/17, Amendment # 5 8/9/2017 with IB 10, AMENDMENT #6 1/16/18

developed pneumonitis should suspend study treatment with BYL719 (alpelisib) immediately and undergo appropriate imaging (high resolution CT scan); and broncho-alveolar lavage and biopsy should be considered if clinically appropriate. Infectious causes of interstitial lung disease should be ruled out. Investigators should follow institutional practice for management of pneumonitis which generally includes treatment with high dose corticosteroids; antibiotic therapy should be administered concurrently if infectious causes are suspected. Consultation with a pulmonologist is highly recommended for any pneumonitis case during the study treatment. BYL719 (alpelisib), capecitabine and radiation (if suspected to be etiologically related to the AE of pneumonitis) should be permanently discontinued in all patients with confirmed pneumonitis.

Consultation with a pulmonologist is highly recommended for any pneumonitis case during the study treatment.

If the pneumonitis is confirmed to be study drug related, BYL719 must be discontinued.

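### A BYL719 hold of about 13 to 28 days that the protocol requires for a non-toxicity reason leaves the patient neither a DLT nor inevaluable, so by implication DLT-free in the cohort count

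*Combined protocol and SAP*

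**What the plan says.** Two rules classify exposure below 67%.

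- Inevaluable (Section 4.1, repeated in Section 17.0): "A patient will be considered inevaluable if they receive <67% of their total intended treatment (BYL719, Capecitabine or Radiation) for non-protocol required reasons".
- DLT (Section 5.2, and the DLT list in Section 4.1): "Patients who receive < 67% of intended BYL719 or capecitabine secondary to treatment related toxicities will also be considered as having a DLT". The Section 4.1 list adds a parenthesis calling these same patients inevaluable. Section 5.2 does not.

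The protocol also mandates a BYL719 hold that need not involve any toxicity. Under Section 4.2.2, when a patient needs a prohibited drug, "BYL719 administration must be interrupted as long as the patient requires therapy with the QT prolonging agent". Only long-term need, "leading to study treatment interruption of > 28 days, the patient must be permanently discontinued from BYL719", ends BYL719 for good. Lost doses stay lost (Section 4.1): "Missed doses of BYL 719 are not made up and BYL719 will be stopped when radiation is completed".

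The exits are limited. Section 4.1 says: "If treatment is held for more than 28 days, then patient should come off study". Replacement during dose finding applies to "patients who are removed from study for reasons other than a DLT, defined in section 5.2, will be replaced". Escalation (Sections 4.1 and 17.0) requires that no DLT is seen in the first three patients after treatment is completed and two weeks of observation have passed. No minimum exposure is set.

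**The concern.** The two rules leave a third case open: a shortfall that the protocol requires and that treatment-related toxicity did not cause. Nothing classifies that patient, and nothing takes the patient out of the cohort.

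The MTD is the primary objective, and three patients without a DLT open the next level. One patient with reduced exposure is a third of that evidence. The 67% threshold shows that the sponsor already regards lower exposure as inadequate for evaluation, and the reason for the shortfall does not change how much the patient reveals about tolerability. Without a rule, evaluability would have to be decided after the patient's outcome is known.

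**Working it through.** **Course length.** Section 4.1 gives 28 fractions, with BYL719 taken once daily from the first to the last day of radiation. Weekday treatment from a Monday is 5 weeks × 5 fractions + 3 fractions, ending on the Wednesday of week 6: 5 × 7 + 3 = 38 days, or 38/7 = 5.43 weeks. This agrees with the 5½ weeks in Section 5.1. A Thursday or Friday start gives 40 days. The plan does not define intended treatment, so 38 to 40 doses is derived from the schedule.

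**Width of the gap.** Exposure = (planned − missed)/planned.

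- 38 doses: 12 missed gives 26/38 = 68.4%, above the threshold. 13 missed gives 25/38 = 65.8%, the first value below it. 28 missed, the longest hold that does not trigger removal, gives 10/38 = 26.3%.
- 40 doses: 14 missed gives 26/40 = 65.0%. 28 missed gives 12/40 = 30.0%.

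The unclassified window is therefore a hold of about 13 to 28 days while radiation continues. Exposure drops below half only from 20 missed doses of 38 (18/38 = 47.4%).

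**Effect on escalation.** A level passes with 0 of 3 DLTs, or with 1 of 3 followed by 0 of 3:

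P(pass) = P(0 of 3) + P(1 of 3) × P(0 of next 3).

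The DLT rates below are assumptions; the documents give none. With full exposure and p = 0.33:

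- P(0 of 3) = 0.67³ = 0.301
- P(1 of 3) = 3 × 0.33 × 0.67² = 0.444
- P(pass) = 0.301 + 0.444 × 0.301 = 0.43

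Now give one of the first three a lower risk q and keep the others at 0.33:

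- P(0 of 3) = 0.67² × (1 − q)
- P(1 of 3) = 2 × 0.33 × 0.67 × (1 − q) + 0.67² × q
- q = 0.20: 0.359 + 0.444 × 0.301 = 0.49
- q = 0.10: 0.404 + 0.443 × 0.301 = 0.54
- q = 0: 0.449 + 0.442 × 0.301 = 0.58

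If risk is instead assumed proportional to exposure, P(pass) is:

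| Assumed DLT rate | All at full exposure | One at 66% | One at 26% | One at zero risk |
|---|---|---|---|---|
| 20% | 0.709 | 0.741 | 0.779 | 0.804 |
| 33% | 0.434 | 0.485 | 0.544 | 0.582 |
| 40% | 0.309 | 0.362 | 0.424 | 0.464 |
| 50% | 0.172 | 0.220 | 0.276 | 0.312 |

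The first results column also applies after the fix, because an under-exposed patient would be replaced.

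**The case against.** **No sentence says the patient counts as DLT-free.** That is correct. A reader might infer that the plan instructs this. It does not; the status follows only because nothing excludes the patient. Two readings might exclude the patient, and neither is secure. One treats the need for a prohibited drug as a reason the protocol does not require. That is strained, since Section 4.2.2 makes the interruption mandatory. The other points out that escalation follows completion of treatment. But a course can be completed with BYL719 interrupted, and no exposure threshold is attached to completion.

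**Other holds look similar but are weak examples.** Section 5.3 says patients suspected to have "developed pneumonitis should suspend study treatment with BYL719 (alpelisib) immediately". No text makes that suspension last 13 days once pneumonitis is excluded, and confirmed cases stop BYL719 permanently. When radiation itself is held for toxicity (Section 4.1), BYL719 runs to the final fraction, so a delayed course may restore the doses. Treatment-related toxicity is in any case covered by the DLT rule.

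**There are other safeguards.** Exclusions 3.2.9 and 3.2.12 screen for problem medications at entry. Section 12.0 withdraws patients for intercurrent illness that significantly affects assessment or requires stopping treatment, and it lets the physician stop treatment in the patient's interest. These narrow the gap, but they do not catch every temporary hold.

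**It is tempting to call such a patient largely untreated or uninformative.** The figures do not support that across the window. Holds of 13 to 18 days leave 20 to 25 of 38 doses, a majority. Section 9.1.5 puts the hyperglycaemia peak around days 8 to 10, so even 10 early doses could span it.

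**The probability shift is conditional on the event occurring.** If 2% to 10% of patients had such a hold (an assumption), the chance of at least one in three is 1 − 0.98³ = 6% to 1 − 0.90³ = 27%. With a shift of about 0.10, the average effect is then roughly 0.006 to 0.03. This stands, and it limits the severity.

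**Conclusion.** The gap is real on the text, and it is the same in Sections 4.1 and 17.0. It is confined to protocol-required, non-toxicity BYL719 holds of about 13 to 28 days, with the Section 4.2.2 QT-drug interruption as the one clear trigger. If it occurs in one of the first three patients, the chance of passing the level rises from 0.43 to 0.49–0.58, assuming a 33% DLT rate and a risk of 20% down to 0% in that patient. The direction rests on lower exposure carrying lower DLT risk.

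A reader might conclude that the MTD will be set too high. The documents do not support that: they give no frequency for such holds, and the event is probably uncommon. The point should be fixed because a stated rule misclassifies a foreseeable case in very small cohorts, but it does not undermine the design.

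**What to change.** In Sections 4.1 and 17.0, replace the inevaluability sentence with one along these lines:

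*A dose-finding patient without a DLT is evaluable for the MTD decision only if at least 67% of intended BYL719, capecitabine and radiation was received, whatever the reason for the shortfall. Otherwise the patient is replaced for the MTD decision and kept in the safety summary. A patient with a DLT, including the DLT for exposure below 67% due to treatment-related toxicity, counts at any exposure.*

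Three wording points belong with it:

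- Reconcile the parenthesis in the Section 4.1 DLT list with Section 5.2, so that toxicity-driven shortfall has a single classification.
- Define intended treatment as a number of planned doses.
- Reconcile Section 5.1 with Section 4.1 on BYL719 when radiation is missed for administrative reasons, because this decides which gaps are protocol-required.

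The cost is an occasional replacement patient and some delay at that level. Three levels of six use at most 18 of the 24 planned patients, which leaves 6 places to absorb replacements, at the expense of the expansion. The evaluability change alters no dose, hold or discontinuation rule.

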4.2 Concomitant medications

In general, the use of any concomitant medication/therapies deemed necessary for the care of the patient is permitted, except as specifically prohibited below and in Appendix F and G and the Investigators Brochure (please know that medical marijuana is included in reference to herbal medications in Appendix G as a prohibited medication on study). All medications and significant non-drug therapies (including blood transfusions) patient is taking at baseline prior to the administration of BYL719 through 30 days after the last dose of BYL719 will be recorded on the Concomitant medications log.

The investigator should instruct the patient to notify the investigational site about any new medications she takes after the start of the study drug.

The patient must be told to notify the investigational site about any new medications he/she takes after the start of the study drug. All medications (other than study drug) and significant non-drug therapies (including physical therapy and blood transfusions) administered during the study must be listed on the Concomitant Medications or the Procedures and Significant Non-Drug Therapies section of the patient record, respectively.

4.2.1 Permitted concomitant therapy

Antiemetics

Use of anti-emetics is allowed. Prophylactic anti-emetics should be started only once the patient experiences nausea or vomiting, at the discretion of the investigator. It is recommended that patients use drugs that do not cause QT prolongation (Appendix F). Please note that some anti-emetics have a known risk for TdP and are prohibited (refer to Appendix G)

Oral hypoglycemic anti-diabetic Agents

Patients who develop diabetes mellitus during the study should be treated according to the ADA (American Diabetes Association) guidance. It is recommended to start treatment with glimepiride, glibenclamide or metformin. Patients receiving oral antidiabetics which are predominantly metabolized by CYP2C9 and CYP2C8, including but not limited to, repaglinide, rosiglitazone, glipizide and tolbutamide, must be carefully monitored for hypoglycemia as BYL719 was found to be moderate reversible inhibitor of these enzymes (refer to Appendix F).

Anticoagulation

Anticoagulants other than warfarin/coumarin derivates may be administered under the discretion of the investigator. However, caution is advised when BYL719 is co-administered with antiplatelet pro-drugs such as clopidogrel, ticlopidine and prasugrel, which require metabolic activation by CYP3A4, CYP2C9 and CYP2C19. BYL719 has the potential to inhibit these enzymes and may therefore decrease the metabolic activation and clinical efficacy of these pro-

drugs. Patients using anti-platetet pro-drugs should be carefully monitored (refer to Appendix F).

Contraceptives

Hormonal contraceptives may be affected by cytochrome P450 interactions, and are therefore not considered effective for this study. For allowed contraception methods, refer to Exclusion Criteria. Highly effective contraception should be maintained throughout the study and for 6 months after study treatment discontinuation.

CYP450 substrates

In vitro studies demonstrate that BYL719 is a time dependent inhibitor of CYP3A4(Ki 5.6 μM, Kinact 0.011 min-1). Reversible inhibition of CYP2C8 (Ki 32 μM), CYP2C9 (Ki 22 μM) and CYP2C19 (IC50 75 μM) was also observed. BYL719 may inhibit metabolic clearance of co-medications metabolized by CYP3A4, CYP2C8, CYP2C9 and CYP2C19, if sufficiently high BYL719 concentrations are achieved in vivo. Investigators, at their discretion, may administer concomitant medications known to be metabolized by or are substrates for CYP3A4/5, CYP2C8, CYP2C9 and CYP2C19. Patients receiving such medications and drugs which have a narrow therapeutic index must be carefully monitored for potential toxicity due to any individual concomitant medications. (refer to Appendix F).

Caution is advised when BYL719 is co-administered with opioid analgesics. Inhibition of opioid metabolism by CYP3A4 can lead to opioid toxicity, including fatal respiratory depression, or an enhanced risk for QTc prolongation. Patients receiving BYL719 and opioid analgesics should be carefully monitored. Synthetic opioids with clinically relevant interactions with CYP3A4 inhibitors include, but are not limited to, propoxyphene, fentanyl, alfentanyl and sufentanil. Use of alfentanyl, a sensitive CYP3A4 substrate with narrow therapeutic window, should be full avoided whenever possible. The use of methadone and levomethadyl is prohibited (refer to Appendix G).

Gastric protection agents

BYL719 is characterized by a pH-dependent solubility. Medicinal products that alter the pH of the upper gastro-intestinal tract may alter the solubility of BYL719 and hence its bioavailability. These agents include, but are not limited to, proton-pump inhibitors (PPI) (e.g., omeprazole), H₂-antagonists (e.g., ranitidine) and antacids. Due to long pharmacodynamic effect of PPIs, i.e. long-lasting reduction of gastric acid production over 36 hours, H₂-antagonists and antacids are recommend to be used over PPIs, whenever possible. Note that some proton pump inhibitors may possibly also inhibit BCRP (refer to Appendix F).

BYL719 should preferably be dosed in a staggered manner, i.e., at least 1 hour before or 10 hours after dosing with a gastric protection agent.

BCRP inhibitors

BYL719 was identified as a substrate for the human breast cancer related protein (BCRP). Co-administration of BYL719 with BCRP inhibitors may possibly increase systemic exposure and/or alter tissue uptake of oral BYL719. The treatment with BCRP inhibitors should be kept as short as possible or, if possible, fully avoided. See Appendix F for Table of Permitted Medications.

Corticosteroids

Chronic dosing of high levels of corticosteroids such as dexamethasone and prednisone may prolong or aggravate hyperglycemia (steroid-induced diabetes). Hyperglycemia is a common adverse event for Pi3K inhibitors like BYL719 and should therefore be used with caution and patients closely monitored.

The patient must be told to notify the investigational site about any new medications she/he takes after the start of the study drug. All medications (other than study drug) and significant non-drug therapies (including physical therapy, herbal/natural medications and blood transfusions) administered during the study must be listed on the Concomitant Medications CRF pages.

